#### 8.3.2 DEFINITION OF SERIOUS ADVERSE EVENTS

Serious adverse events as a result of the study intervention will be classified by the attendings. As the intervention in study is a standard of care drug for pain, we do not expect adverse events.

#### 8.3.3 CLASSIFICATION OF AN ADVERSE EVENT

##### 8.3.3.1 SEVERITY OF EVENT

Severity will be graded by the PI and attendings, if required.

### 8.3.3.2 RELATIONSHIP TO STUDY INTERVENTION/EXPERIMENTAL MANIPULATION

Adverse events related of the study intervention will be classified as related or not related by the PI and other attendings.

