## 1 PROTOCOL SUMMARY

### 1.1 SYNOPSIS

Title:	Transabdominal plane (TAP) Blocks for Laparoscopic Inguinal Hernia Repair
Grant Number:	
Study Description:	Inguinal hernias are bulges in the groin region that arise from weaknesses in the abdominal wall. Often, due to discomfort, pain or cosmetic dissatisfaction, these hernias must be surgically repaired. The use of a transabdominal plane (TAP) block—a local injection given in the abdomen to block pain receptors on nerves—during surgery can presumably decrease postoperative pain. The aim of our study is to investigate whether the use of a TAP block can decrease the use of opioids and pain scores after surgery.
Objectives*:	The aim of our study is to examine outcomes and pain control after surgery in patients who underwent laparoscopic inguinal hernia repair (IHR) with the use of perioperative transabdominal plane (TAP) block. Research Question: Does transabdominal plane block improve pain when undergoing inguinal hernia repair?
Endpoints*:	To evaluate whether preoperative TAP blocks improve pain score (primary end point) and decrease opioid use (secondary endpoint) after an inguinal hernia repair. Other end points- complications after surgery.
Study Population:	We will be enrolling 100 patients from Mount Sinai Hospital undergoing laparoscopic inguinal hernia repair.
Phase* or Stage:	
Description of Sites/Facilities Enrolling Participants:	All enrollment will occur at one site (Mount Sinai Hospital) at Faculty Practice Associates and Emergency Department.
Description of Study Intervention/Experimental Manipulation:	The study intervention is the administration of a TAP Block (0.25% bupivacaine or placebo (Saline). For patients weighing <100 kg, they will receive a total of 50 mL (25 mL on each side of the abdominal wall). If patients weigh >100 kg, they will receive a total of 60 mL (30mL on each side of the abdominal wall). The TAP plane is identified using ultrasound. All anesthesiologists working with the surgical attendings involved in this study have been trained in this technique; it is a routine part of their practice. Anesthesiologists will be performing the block.
Study Duration*:	2 Years
Participant Duration:	2 Weeks

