## 4 STUDY DESIGN

### 4.1 OVERALL DESIGN

After receiving approval for the study, we will conduct a prospective single institution randomized clinical trial assessing if using a TAP block perioperatively can reduce pain scores after surgery. Other endpoints include whether there are differences in pain medication usage and complications.

Patients will be screened by research team members and attending surgeons. If the patient is interested, we will consent them for the study after they understand the study details, procedures, and expectations. We will then consent using IRB approved study consent forms and procedures. Patients will undergo a laparoscopic inguinal hernia repair according to standard procedures. Our study will assess if a TAP block impacts pain scores. Patients will be randomized to receive the intervention or placebo. Sequentially numbered sealed opaque envelopes with group allocation inside will alert the anesthesiologist/ surgeon to order Tap block composed of 0.25% bupivacaine or placebo (normal saline).

Inguinal hernia repair will be performed in standard fashion that each individual surgeon is familiar with. No additional tests or blood work outside the standard of care for IHR will be performed for research purposes. In addition, some patients will be given TAP blocks before surgery to help in pain management. In addition, patients will be discharged with a worksheet on which they are to record analgesic use and pain scores on postoperative days one, two, three and four. They are expected to bring the completed log to their two-week follow up visit with their surgeon. Patients may also expect to receive a phone call from a member of the surgical team to remind them to record these metrics.

The TAP block is done pre-procedure using 0.25% bupivacaine. If patients weigh<100 kg, they will receive a total of 50 mL (25 mL on each side of the abdominal wall). If patients weigh>100 kg, they will receive a total of 60 mL (30mL on each side of the abdominal wall). The TAP plane is identified using ultrasound. All anesthesiologists (not surgeons) working with the attendings involved in this study have been trained in this technique; it is a routine part of their practice. It is anesthesiologists who will be performing the block.

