### 8.3.3.3 EXPECTEDNESS

A clinician with appropriate expertise in anesthesiology/surgery will be responsible for determining whether an adverse event (AE) is expected or unexpected. An AE will be considered unexpected if the nature, severity, or frequency of the event is not consistent with the risk information previously described for the study procedures.

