### 8.3.4 TIME PERIOD AND FREQUENCY FOR EVENT ASSESSMENT AND FOLLOW-UP

After notification of an event, the PI will be alerted regarding the event to classify as related or unrelated to the intervention.

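### Clinicians who may know the arm can classify harms in a trial called double blind, and relatedness decides what counts as an adverse event and reaches the IRB

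*Combined protocol and SAP*

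**What the plan says.** Section 4.1 describes how the allocation is acted on: "Sequentially numbered sealed opaque envelopes with group allocation inside will alert the anesthesiologist/ surgeon to order Tap block", with either bupivacaine or saline then ordered. Sections 4.2 and 6.3 call the trial double blind. Section 6.3 rests the masking on equal quantities of the two products, and the only role it masks by name is the data analyst.

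Section 8.3 assigns the judgements on harms as follows:

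- Seriousness (8.3.2): "Serious adverse events as a result of the study intervention will be classified by the attendings".
- Severity (8.3.3.1): "Severity will be graded by the PI and attendings, if required".
- Relatedness (8.3.3.2): events "will be classified as related or not related by the PI and other attendings". Section 8.3.4 adds that, on notification, "the PI will be alerted regarding the event to classify as related or unrelated to the intervention".
- Expectedness (8.3.3.3): "A clinician with appropriate expertise in anesthesiology/surgery will be responsible for determining whether an adverse event (AE) is expected or unexpected".

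None of these sections says what the person judging may know about the arm.

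**The concern.** Relatedness is a matter of opinion, and the plan gives no criteria for it. A classifier who knows that the patient received saline has a ready reason to answer not related, even when the needle could have caused the event. Under this plan that answer has consequences: an event judged not to be caused by the intervention falls outside the adverse event definition and outside IRB reporting. At stake is whether injection harms are classified and reported in the same way in both arms.

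**Working it through.** There is no plan figure to reproduce. The check sets the sections side by side.

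**1. Who may learn the arm.** Whoever acts on the envelope must know the product in order to order it. Equal volume can mask the patient, or someone handed a prepared syringe, but not the person who orders by name. Section 4.1 names that person as anesthesiologist/surgeon and does not say which.

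**2. Who judges.** Section 1.1 identifies the attendings as surgical: "All anesthesiologists working with the surgical attendings involved in this study have been trained in this technique". The wording of 8.3.3.2 counts the PI among the attendings. The overlap with step 1 depends on how the slash is read:

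| Reading of Section 4.1 | Judgements that a clinician who knows the arm could make |
|---|---|
| The surgeon, or both, learn the arm | Seriousness, severity, relatedness, expectedness |
| Only the anesthesiologist learns the arm | Expectedness, if an anesthesiologist is chosen; surgical judges could stay masked |

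The plan does not choose between these readings. Under either, nothing in Section 8.3 excludes the clinician who learned the arm from classifying that patient's event.

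**3. What the relatedness call controls.** Section 8.3.1 defines an adverse event as one caused by the study intervention. Sections 8.3.5 and 8.3.6 send to the IRB only events due to it. A not-related answer therefore removes the event from both.

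**4. What the intervention is.** Section 6.1.1 names bupivacaine alone, while the synopsis in Section 1.1 includes saline in its description of the intervention. Both arms receive an injection (Section 6.1.2). Section 2.3.1 lists bowel perforation as a risk of the injection itself, separately from local anesthetic systemic toxicity (LAST). A perforation after saline is thus a harm of the trial procedure, yet on a literal reading of 6.1.1 it is not due to the intervention.

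**5. What does not depend on the call.** Patients record their own pain scores. Section 8.2 has all complications and events tracked, with no relatedness filter. Section 9.4.9 compares complication types and rates as an exploratory analysis, and Section 9.4.4 plans no safety analysis.

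**6. Size.** The plan gives no complication or adverse event rate by arm and no basis for how often a classifier would answer related. Its only numerical risk is LAST, below 1% of anesthetic injections. With 100 patients at 1:1, each arm has 100 / 2 = 50 patients, so fewer than 0.01 × 50 = 0.5 LAST events are expected in the bupivacaine arm. Perforation is called minimal, with no figure. The size of any arm-dependent classification cannot be calculated from these inputs.

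**The case against.** The strongest reply is that this follows from an unclear blinding procedure. If someone uninvolved prepared the syringe and every classifier were masked, the question of who judges would disappear. That is right, and the fix below asks for the blinding description to be settled. The definition of related would still need repair: a masked classifier cannot apply a definition that covers bupivacaine only.

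Second, the overlap between those told the arm and those who judge is possible but not shown. Section 4.1 may mean that only the anesthesiologist opens the envelope. This stands as a limit. Section 10.1.5 on key roles was also not available to me, so an assignment made there could narrow the point.

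Third, a reader might infer that arm-dependent judgement would produce a false harm difference in the trial's results, and might put a ratio on it by assuming event and classification rates. The documents do not support that. No planned comparison uses relatedness, the complication comparison takes events without that filter, and the listed risks are below 1% or minimal, so any such ratio would reflect the assumed rates alone. Nor does the point reach the patient-reported primary endpoint.

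**Conclusion.** The point holds in a limited form. The plan allows a clinician who may know the arm to classify seriousness, severity, relatedness and expectedness. Its definitions also let a harm of the saline injection be called not related and so escape reporting. The effect falls on AE and SAE classification and IRB reporting, and its size is unknown. The conclusion rests on two things the plan leaves open: that the surgeon as well as the anesthesiologist may see the allocation, and that the intervention may be read as bupivacaine alone. The change is worth making because it is cheap and bears on safety reporting. The planned efficacy analysis does not depend on it.

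**What to change.** Amend Sections 8.3.2 to 8.3.4, including the step in 8.3.4 that sends each event to the PI:

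- Seriousness, severity, relatedness and expectedness are classified for the trial record by the PI or another existing investigator who did not open that patient's envelope and did not order or give that block.
- The classifier works from an event description that omits the arm, and signs before any unmasking.
- Related means related to the injection procedure or to its content, in either arm. Align the descriptions of the intervention in Sections 1.1 and 6.1.1 with this.
- Treating clinicians keep full access to the arm for patient care.

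Reconcile Sections 4.1 and 6.3 by stating who opens the envelope, who orders and prepares the syringe, and hence who is masked.

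The cost is a few sentences. No new post is implied, since the plan already refers to the PI and other attendings, though it does not say how many there are. The small downside is that a colleague, not the treating clinician, signs the classification, and where the PI was involved in the case another investigator must do it.

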### 8.3.3.3 EXPECTEDNESS

A clinician with appropriate expertise in anesthesiology/surgery will be responsible for determining whether an adverse event (AE) is expected or unexpected. An AE will be considered unexpected if the nature, severity, or frequency of the event is not consistent with the risk information previously described for the study procedures.

### 8.3.4 TIME PERIOD AND FREQUENCY FOR EVENT ASSESSMENT AND FOLLOW-UP

After notification of an event, the PI will be alerted regarding the event to classify as related or unrelated to the intervention.

### 8.3.5 ADVERSE EVENT REPORTING

Adverse events due to study intervention will be reported to IRB.

### 8.3.6 SERIOUS ADVERSE EVENT REPORTING

Serious adverse events due to study intervention will be reported to IRB.

### 8.3.7 REPORTING EVENTS TO PARTICIPANTS

N/A

### 8.3.8 EVENTS OF SPECIAL INTEREST

N/A

### 8.3.9 REPORTING OF PREGNANCY

Pregnant women will be excluded from the study.

## 8.4 UNANTICIPATED PROBLEMS

### 8.4.1 DEFINITION OF UNANTICIPATED PROBLEMS

N/A

### 8.4.2 UNANTICIPATED PROBLEMS REPORTING

N/A

### 8.4.3 REPORTING UNANTICIPATED PROBLEMS TO PARTICIPANTS

N/A

## 9 STATISTICAL CONSIDERATIONS

### 9.1 STATISTICAL HYPOTHESES

- Primary Endpoint(s):

We hypothesize that patients randomized to the intervention will have lower pain scores as compared to the placebo arm.

- Secondary Endpoint(s):

We hypothesize that patients randomized to the intervention will have lower intake of opioid and as compared to the placebo arm.

### 9.2 SAMPLE SIZE DETERMINATION

Based on previous clinical trials using a pain medication intervention prior to surgery, our sample of 100 will be enough to detect a difference, should one exist. Moreover, the intervention and placebo will be administered randomly with an overall ratio of 1:1 to maximize power for analysis.

### 9.3 POPULATIONS FOR ANALYSES

Intention to treat analysis will be used for the study. Other sensitivity analyses will include analyses for treatment as administered.

### 9.4 STATISTICAL ANALYSES

#### 9.4.1 GENERAL APPROACH

For descriptive analyses categorical variables will be described using the frequency and proportions. Continuous variables will be described using median and the interquartile range (Q1, Q3). All p-values of statistical tests will be two-tailed with a  $p < 0.05$  considered statistically significant.

#### 9.4.2 ANALYSIS OF THE PRIMARY ENDPOINT(S)

The primary endpoint of differences on pain score will be analyzed using the Wilcoxon rank sum test or Mann-Whitney U test.

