## 3 OBJECTIVES AND ENDPOINTS

OBJECTIVES	ENDPOINTS	JUSTIFICATION FOR ENDPOINTS	PUTATIVE MECHANISMS OF ACTION
Primary			
Do TAP blocks improve pain score?	Change in pain score for the intervention versus placebo groups.	Assessing causal effect of TAP block on pain levels through the RCT design is the gold standard approach.	
Secondary			
Do TAP blocks decrease opioid and other pain medication use after surgery?	Assessing number/volume of pain medication.	TAP blocks should directly impact pain medications usage.	
Tertiary/Exploratory			
Does TAP block usage affect complications after surgery?	Assessing complication rate differences between the intervention and placebo groups with regards to complications.	Complications can differ based on treatment. We want to assess if complications rates differ between the two groups.	

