Patients will be discharged with a worksheet /survey on which they are to record analgesic use and pain scores on postoperative days one, two, three and four. They are expected to bring the completed log to their two-week follow up visit.

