#### 4.4 END-OF-STUDY DEFINITION

End-of-study is defined as completing the intervention and any portion of worksheet. Study times are expected to take place during a 2 week time period.

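### The primary rank test names no day, summary or missing-day rule although any portion of the day 1–4 worksheet suffices; averaging recorded days could bias it either way, and the mixed model promised in Section 2.2 is absent from 9.4

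*Combined protocol and SAP*

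**What the plan says.** - **Measurement.** Section 4.1 sends patients home with a worksheet to "record analgesic use and pain scores on postoperative days one, two, three and four". They bring it to the two-week visit. A reminder call is possible.
- **Completion.** Section 4.4: "End-of-study is defined as completing the intervention and any portion of worksheet".
- **Endpoint.** Section 3 gives the primary endpoint as "Change in pain score for the intervention versus placebo groups". It names no scale, baseline, day or summary.
- **Primary test.** Section 9.4.2: "The primary endpoint of differences on pain score will be analyzed using the Wilcoxon rank sum test or Mann-Whitney U test". The section says nothing more.
- **Population.** Section 9.3: "Intention to treat analysis will be used for the study". It adds that sensitivity analyses will include one by treatment as administered. It has no rule for missing scores.
- **Longitudinal analysis.** Section 2.2 criticises published trials for simple tests that ignore repeated measurement. It says that mixed effects models with a correlation structure will be used for pain scores and opioid consumption, in addition to the simple tests. No part of Section 9.4 contains these models.

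**The concern.** A two-sample rank test takes one number per patient. The worksheet supplies up to four, and some patients will supply fewer. The plan does not say how four, three, two or one recorded scores become that number, so the rule would be chosen after the data are in.

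The choice matters because pain normally falls over the first days after surgery. A patient who stopped recording after day 2 and is scored on the mean of recorded days is scored on the worst days only. That value is then ranked against values that also include the easier days 3 and 4. If more patients stop early in one arm, that arm looks worse although true pain is the same. Stopping could plausibly differ: an effective block changes pain, and pain may affect diary-keeping, with either comfortable or suffering patients stopping first. The primary result could then miss a real benefit or show a false one.

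**Working it through.** **Inputs from the plan.** The sample is 100 (Section 9.2: "our sample of 100 will be enough to detect a difference, should one exist") at an "overall ratio of 1:1 to maximize power for analysis", so 50 per arm. Section 9.4.1 sets a 0.05 threshold and states "All p-values of statistical tests will be two-tailed". There are four recording days.

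**The plan's own figure.** The 100 cannot be reproduced, because no effect size, SD, power or dropout rate is given. At 50 per arm, 80% power corresponds to a standardised difference of 0.56, or about 0.57 for the rank test under normality.

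**Assumed inputs (none is in the documents).** 0–10 pain scale; SD 2 on each day; within-patient correlation 0.6; daily means 5, 4, 3, 2; a partial log stops after day 2; stopping is random within an arm. The true benefit, where there is one, is 0.97 points. The SD of a four-day mean is 2 × √[(1 + 3 × 0.6)/4] = 1.67, and 0.97/1.67 = 0.58, so this is close to the benefit that complete logs detect with 80% power.

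**Bias by hand, mean of recorded days.** A full log averages (5+4+3+2)/4 = 3.5. A log stopped after day 2 averages (5+4)/2 = 4.5. Bias = (stopping rate on bupivacaine − stopping rate on saline) × (4.5 − 3.5).

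- 30%/10%: 0.20 × 1.0 = +0.20 points, against the block
- 10%/30%: −0.20 points, in favour of the block
- 20%/10%: +0.10 points
- 20%/20%: 0
- 30%/10% with a 0.5-point daily fall: 0.20 × 0.5 = +0.10 points
- 30%/10% with a 1.5-point daily fall (6, 4.5, 3, 1.5): 0.20 × (5.25 − 3.75) = +0.30 points

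**Simulation of the same setting (4,000 trials per scenario for the 1- and 1.5-point rows at 30%/10% and 10%/30%).** Rank test on the mean of recorded days:

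| Daily fall | Stopping, bupivacaine/saline | Bias | False positives | Power |
|---|---|---|---|---|
| 1 point | 30%/10% | +0.20 | 8.0% | 57% |
| 1 point | 10%/30% | −0.19 | 8.6% | about 90% (inflated by the bias) |
| 1 point | 20%/10% | +0.10 | 5.6% | – |
| 0.5 point | 30%/10% | +0.09 | 5.7% | – |
| 1.5 points | 30%/10% | not tabulated | 12.1% | 44% |

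Repeat runs of the two 1-point rows at 30%/10% and 10%/30% put false positives between 7% and 9%. With each score centred on its day before averaging, false positives were 5.0% and power 78% at 30%/10% with the 1-point fall, and 5.1% and 78% with the 1.5-point fall.

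**A single fixed day, same inputs.** Days are not mixed and the false-positive rate stays near 5%. Power is about 65% on day 1 and 54–56% on day 4, against 78–79% for the day-adjusted analysis of all days. Day 4 is lower because the stopped logs have no day 4 score.

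**A second set of assumptions (2,000 trials per scenario).** Between-patient SD 1.5, within-patient SD 1.2, whole-number scores, partial logs holding the first one or two days, 40% partial on bupivacaine and 10% on saline, no true effect:

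- Means 5, 4, 3, 2: bias +0.36 and 16% false positives for the mean of recorded days; +0.70 and 37% for the last recorded day.
- Means 4, 3.5, 3, 2.5: +0.17 and 7%; +0.36 and 16%.
- Rates reversed: the bias changes sign at nearly the same size.
- 30% partial in both arms with the same days kept: no bias, and 4.0–5.6% false positives. On the steeper course, power for a 1-point benefit by the mean of recorded days fell from 86% to 78%.
- 30% partial in both arms, but late days kept on bupivacaine and early days on saline, steeper course: bias −0.70 and 48% false positives. Equal rates therefore protect only if the same days are missing.

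**Four daily tests.** These do not mix days, but without adjustment the chance of at least one false positive is up to 1 − 0.95⁴ = 18.5% (independent tests; lower when correlated).

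**The case against.** The strongest reply is that the plan never says it will mix days. Section 4.4 defines when a participant has finished the study; it does not say that a partial log is complete data for analysis. A reader might infer from 4.4 and 9.4.2 together that scores from different days will be pooled, but a test on one fixed day, or on each day, fits 9.4.2 equally well. This stands: day-mixing is conditional on a choice that the plan leaves open.

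A reader might also infer that any single-day test discards the partial logs and so breaks intention to treat. It does so only if the chosen day is a missing one. A day 1 test loses nobody when logs stop after day 2.

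Nothing in the documents suggests that stopping will differ by arm. Patients are meant to be blinded and may get reminder calls. The milder scenarios give negligible inflation. That also stands, and limits the size of the point.

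Finally, Section 2.2 does commit to mixed effects models for pain, so it would be wrong to say that the sponsor planned no longitudinal analysis. But those models are described as additional to the simple tests and are missing from 9.4, so they do not repair the primary test as written. Nor should the as-administered analysis be called the only sensitivity analysis planned: 9.3 says that such analyses will include it.

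**Conclusion.** The concern holds in conditional form. The plan accepts partial logs and specifies a test that needs one value per patient, but fixes neither the day, the summary nor a missing-day rule. If recorded days are averaged or the last one is used, and stopping differs by arm, the primary comparison is biased in whichever direction the stopping runs. Under SD 2 and correlation 0.6, the size for averaging runs from about 0.1 point with under 6% false positives (mild inputs) to about 0.2 points with 7–9% (30%/10% stopping, 1-point daily fall), and more on a steeper course. With equal stopping on the same days there is no bias, only some loss of power. If one fixed day is used, there is no day-mixing, but power drops by roughly 13 to 25 percentage points against using all days (78 − 65 = 13; 79 − 54 = 25).

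The documents do not support the stronger conclusion that the primary result will be biased. Every SD, correlation, slope and stopping rate here is an assumption. What the documents do establish is the gap in 9.4.2 and the mismatch between 2.2 and 9.4.

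**What to change.** In 9.4.2, make the primary estimate the average difference between arms over days 1–4 from a repeated-measures mixed model. Use day as a categorical factor, within-patient correlation and all recorded days. This carries the commitment in Section 2.2 into 9.4. If a rank analysis is preferred, rank patients on the mean of day-centred scores (each score minus the pooled mean for its day). Keep the simple rank test as supportive, with its day or summary named. Align the endpoint wording in Section 3 with the quantity estimated.

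Optionally, add to 9.3 a sensitivity analysis for randomized patients with no score at all, for example assigning them the worst rank. This covers empty logs; it does not address partly filled ones.

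The cost is SAP wording and a few hours of analysis, with no new data. The model assumes that missing scores are missing at random given the recorded ones. Neither it nor day-centring fully handles stopping that depends on unrecorded pain, and the SAP should say so.
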